18.3 Clinical Laboratory and Other Abnormal Assessments as AEs and SAEs

Abnormal laboratory findings (e.g. clinical chemistry, haematology, urinalysis) or other abnormal assessments (e.g. ECG, vital signs) that are judged by the investigators as clinically significant will be recorded as AEs or SAEs if they meet the definition of an AE, as defined in Section 18.1 or SAE as defined in Section 18.2. Clinically significant abnormal laboratory findings or other abnormal assessments that are detected during the study or are present at baseline and significantly worsen following the start of the study will be reported as AEs or SAEs. However, clinically significant abnormal laboratory findings or other abnormal assessments that are associated with a disease reported in the medical history, unless judged by the investigators as more severe than expected for the subject's condition, or that are present or detected at the start of the study and do not worsen, will not be reported as AEs or SAEs.

The investigators will exercise their medical and scientific judgement in deciding whether an

abnormal laboratory finding or other abnormal assessment is clinically significant.

18.4 Time Period, Frequency, and Method of Detecting AEs and SAEs

All adverse events will be recorded between the time of consent and follow-up visits. Each participant will be monitored regularly by the investigators and study personnel for adverse events occurring throughout the study.

18.5 Recording of AEs and SAEs

When an AE/SAE occurs, it is the responsibility of the investigators to review all documentation (e.g. hospital progress notes, laboratory, and diagnostic reports) relative to the event. The investigators will then record all relevant information regarding an AE/SAE into the Case Report Form for that participant.

For each adverse event, start and stop dates, action taken, outcome, intensity (see Section 18.8.1) and relationship to narrow band UVB phototherapy (causality) (see Section 18.8.2) must be documented. If an AE changes in frequency or intensity, a new entry of the event must be made in the Case Report Form for that participant.

The investigators will attempt to establish a diagnosis of the event based on signs, symptoms, and/or other clinical information. In the absence of a diagnosis, the individual signs/symptoms should be documented. All details of any treatments initiated due to the adverse event should be recorded in the Case Report Form for that participant.

18.6 Prompt Reporting of SAEs to the Data Safety Monitoring Board

Once the investigators and the Co-ordinating Principal Investigator become aware that an SAE has occurred in a study participant, they will immediately notify the Data Safety Monitoring Board. The SAE form must be completed as thoroughly as possible with all available details of the event, signed by the investigator (or appropriately qualified designee), and faxed to the independent neurologist on the Data Safety Monitoring Board ([name]) within 24 hours of first becoming aware of the event.

If the investigators do not have all information regarding an SAE, they will not wait to receive additional information before notifying the Co-ordinating Principal Investigator of the event and completing the form. The form will be updated when additional information is received.

The investigator will always provide an assessment of causality at the time of the initial report as described in Section 18.8.2, "Assessment of Causality". If data obtained after reporting indicates that the assessment of causality is incorrect, then the SAE form may be appropriately amended, signed and dated, and resubmitted to the Co-ordinating Principal Investigator.

After notifying the Data Safety Monitoring Board, the Co-ordinating Principal Investigator must inform the Ethics Committee of any SAEs.

The investigators, and others responsible for participant care, should institute any supplementary investigations of serious adverse events based on their clinical judgement of the likely causative factors. This may include seeking further opinion from a specialist in the field of the adverse event. Members of the study team responsible for participant care may also request extra tests. If a subject dies, any post-mortem findings, including histopathology will be provided to the Co-ordinating Principal Investigator and the Data Safety Monitoring Board. No medical help, diagnosis, or advice should be withheld from the subject due to an inability to contact the Co-ordinating Principal Investigator.

18.7 Expeditable Events

Expeditable events are those adverse events that are **CAUSALLY** related to narrow band UVB phototherapy, **AND** that are both **SERIOUS** (see Section 18.2) and **UNEXPECTED** (SUSAR, Suspected Unexpected Serious Adverse Reaction)(see Section 18.8.3). Such events are subject to expedited reporting to regulatory authorities and will be reported within the stipulated timelines by the Co-ordinating Principal Investigator.

18.8 Evaluating AEs and SAEs

18.8.1 Assessment of Intensity

The investigators will make an assessment of intensity for each AE and SAE reported during the study.

The assessment will be based on the investigator's clinical judgement. The intensity of each AE and SAE recorded in the Case Report Forms should be assigned to one of the following categories:

• Mild: An event that is easily tolerated by the subject, causing minimal

and not interfering with everyday activities.

• Moderate: An event that is sufficiently discomforting to interfere with normal

activities.

• **Severe:** An event which is incapacitating and prevents normal everyday activity.

An AE that is assessed as severe should not be confused with a SAE. Severity is a category utilised for rating the intensity of an event; and both AEs and SAEs can be assessed as severe. An event is defined as "serious" when it meets one of the pre-defined outcomes as described in Section 18.2 "Definition of an SAE".

18.8.2 Assessment of Causality

The Co-ordinating Principal Investigator is obligated to assess the relationship between the intervention and the occurrence of each AE/SAE, in consultation with Professors [name] and [name], and [name]. Alternative causes, such as natural history of the underlying diseases,

concomitant therapy, other risk factors, and the temporal relationship of the event to the administration of narrow band UVB phototherapy will be considered and investigated.

The causal relationship to UVB phototherapy should be assessed using the following classifications:

Not Related In the Investigator's opinion, there is not a causal relationship between UVB

phototherapy and the adverse event.

Unlikely The temporal association between the adverse event and UVB phototherapy is

such that UVB phototherapy is not likely to have any reasonable association with

the adverse event.

Possible The adverse event could have been caused by the study participants's clinical

state or UVB phototherapy.

Probable The adverse event follows a reasonable temporal sequence from the time of

UVB phototherapy, abates upon discontinuation of UVB phototherapy and cannot be reasonably explained by the known characteristics of the study

participants's clinical state.

Definitely The adverse event follows a reasonable temporal sequence from the time of

UVB phototherapy or reappears when UVB phototherapy is reintroduced.

There may be situations when an SAE has occurred and a member of the study team has minimal information to include in the initial report to the Co-ordinating Principal Investigator, and the Data Safety Monitoring Board. However, it is very important that the member of the study team always makes an assessment of causality for every event prior to transmission of the SAE form to the Co-ordinating Principal Investigator. Investigators may change their opinion of causality in light of follow-up information, amending the SAE form accordingly. The causality assessment is one of the criteria used when determining regulatory reporting requirements.

18.8.3 Assessment of Expectedness

Expected An adverse reaction, the nature or severity of which is consistent with the

Participant Information Sheet for narrow band UVB phototherapy.

Unexpected An adverse reaction, the nature or severity of which is not consistent with

information in the Participant Information Sheet for narrow band UVB

phototherapy.

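### The Expected and Unexpected definitions in 18.8.3 are not mutually exclusive, so the expedited-reporting rule in 18.7 does not give every serious related event a single answer

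*Protocol*

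**What the plan says.** Section 18.8.3 of the protocol gives two definitions, both judged against the Participant Information Sheet for narrow band UVB phototherapy:

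- Expected: "An adverse reaction, the nature or severity of which is consistent with the" sheet.
- Unexpected: "An adverse reaction, the nature or severity of which is not consistent with" the information in the sheet.

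Section 18.7 uses this classification. An event is expeditable when it is causally related to phototherapy, serious and unexpected ("SUSAR, Suspected Unexpected Serious Adverse Reaction"), and 18.7 points to 18.8.3 for the last condition. The consequence is stated there: "Such events are subject to expedited reporting to regulatory authorities and will be reported within the stipulated timelines by the Co-ordinating Principal Investigator".

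A separate route in 18.6 does not depend on expectedness. Once the investigators learn of a serious adverse event, "they will immediately notify the Data Safety Monitoring Board", with the form due within 24 hours, and after that "the Co-ordinating Principal Investigator must inform the Ethics Committee of any SAEs". Section 19.2 has the Board review each serious adverse event individually and unblinded.

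**The concern.** A two-way classification that decides whether a report is sent should put each event in one class. Here the two definitions differ only by the word *not*, while *or* joins the two attributes in both. An event that agrees with the sheet on one attribute and disagrees on the other therefore meets both.

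What is at stake is the expedited report to regulatory authorities. Section 18.2 already defines a serious adverse event as one resulting from UVB phototherapy, so causality is largely built into seriousness. Expectedness is then the main condition left to settle before an event becomes expeditable. If one assessor reads the Expected line and stops, and another reads the Unexpected line, they can label the same event in opposite ways, and each can point to the protocol. Section 18.8.1 grades intensity separately from seriousness, so a reaction more intense than described is something assessors will have on record.

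**Working it through.** No number in the protocol is involved, so the check is logical.

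**Inputs.** Let N mean that the nature of the reaction is consistent with the Participant Information Sheet, and S that its severity is. From 18.8.3 as written:

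- Expected = N or S
- Unexpected = (not N) or (not S)

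From 18.7: expeditable = related and serious and Unexpected.

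**As written.**

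| Nature consistent | Severity consistent | Meets Expected | Meets Unexpected |
|---|---|---|---|
| yes | yes | yes | no |
| yes | no | yes | yes |
| no | yes | yes | yes |
| no | no | no | yes |

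Two of the four combinations meet both definitions. Sections 18.7 and 18.8 contain no tie-break.

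**How realistic the two mixed rows are.** The second row is a reaction of a type the sheet lists, at a severity it does not describe. That can plainly arise. The third row needs a reaction the sheet does not list but whose severity the sheet nonetheless matches. A sheet that omits a reaction will normally give no severity for it, so this row is close to empty. The practical overlap is therefore mainly one row. A count of rows is not an event frequency, and the protocol gives no rate from which to derive one.

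**Can the same connective be rescued?** Suppose *or* is read as *and* in both lines. Then Expected = N and S, and Unexpected = (not N) and (not S). The overlap disappears, but the two mixed rows now meet neither definition. Using one connective in both lines gives either an overlap or a gap.

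**With different connectives.** Let Expected = N and S, and leave Unexpected = (not N) or (not S).

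| Nature consistent | Severity consistent | Class |
|---|---|---|
| yes | yes | Expected only |
| yes | no | Unexpected only |
| no | yes | Unexpected only |
| no | no | Unexpected only |

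The classes are now exact complements, with no overlap and no gap.

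**The case against.** The strongest reply is that 18.7 is triggered by meeting the Unexpected definition and contains no exemption for an event that also meets the Expected one. A reaction of listed type and unlisted severity meets the Unexpected line, so on one fair reading it is already expeditable. To miss it, an assessor would have to stop at the first definition and disregard the second. This stands. A reader might infer that such a reaction is properly recorded as expected and so falls outside expedited reporting. The text does not support that: it leaves the class undetermined.

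A reader might also infer that a serious reaction could go unseen. The documents do not support that either. Sections 18.6, 19.2 and 24.2 take serious adverse events to the Board and the Ethics Committee whatever their expectedness, and the Board may recommend stopping the study at any time. Only the additional regulatory route is exposed.

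Two further points limit the size. Phototherapy is given at one centre to 30 planned recipients, and the Co-ordinating Principal Investigator both assesses causality and makes the expedited reports, so conflicting labels across sites are unlikely. Section 18.8.3 does not, however, say who judges expectedness. And the Participant Information Sheet is not among the documents, so any particular reaction offered as an example is hypothetical. The overlap itself holds whatever the sheet lists.

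None of this removes the contradiction. Both definitions and the cross-reference to them are in the protocol, and a statistical analysis plan would not be expected to repair them.

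**Conclusion.** The point holds as a drafting defect in an operative safety-reporting rule. The two definitions overlap in two of four logical combinations, of which one is realistic, and nothing says which label prevails. An assessor who relies on the Expected line could leave a related serious event out of expedited reporting to regulatory authorities, although the same event also meets the Unexpected line.

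The consequence is confined to that one route, and no endpoint, estimate, sample size or analysis is touched. The conclusion about the wording assumes only that *or* carries its ordinary inclusive meaning. How often it would matter cannot be derived from the protocol. The correction is still worth making, because whether a report is sent should not depend on which of two definitions is read first.

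**What to change.** In 18.8.3, define Expected as an adverse reaction whose nature *and* severity are both consistent with the Participant Information Sheet. Leave the Unexpected definition as it is, with *or*. Add one sentence stating that a reaction more severe than the sheet describes is unexpected. Carry the same wording into any guidance that accompanies the serious adverse event form. Section 18.7 then needs no change.

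The cost is a small wording change, submitted as a protocol amendment for ethics approval under 24.7, and possibly a few more expedited reports.

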18.9 Follow-up of AEs and SAEs

After the initial AE/SAE report, the investigators are required to proactively follow each subject and provide further information to the Co-ordinating Principal Investigator on the participant's condition. All AEs and SAEs documented at a previous visit/contact and are designated as ongoing, will be reviewed at subsequent visits/contacts.

All AEs and SAEs will be followed until resolution, until the condition stabilises, until the event is otherwise explained, or until the participant is lost to follow-up. Once resolved, the appropriate AE/SAE Case Report Form page(s) will be updated. Members of the study team will ensure that follow-up includes any supplemental investigations as may be indicated to elucidate the nature and/or causality of the AE or SAE. This may include additional laboratory tests or investigations, histopathological examinations, or consultation with other health care professionals.

New or updated information will be recorded on the originally completed SAE form, with all changes signed and dated by the investigator. The updated SAE form should be resent to the Coordinating Principal Investigator.

19. Data Analysis and Statistical Considerations

19.1 Intention to treat-definition

Participants who have undergone 2 weeks (6 sessions) of narrow band UVB phototherapy will qualify for intention-to-treat analysis.

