8.2 Expected duration of participation in the trial – Time Frame

CIS patients will be invited to join the trial for 12 months. After agreeing to join the trial, participants will be randomized into two groups. Participants in one group will receive narrow band UVB phototherapy which will be administered 3 times per week for 8 weeks. They will also wear a UVB dosimeter. Participants in the other group will not receive phototherapy but will wear a UVB dosimeter for 8 weeks. Blood will be taken from all participants for biomarker analysis at baseline (before phototherapy commences), and 1 week, and 1, 2 (ie when phototherapy ceases), 3, 6 and 12 months after initiation of phototherapy (see Appendix 1).

One group of the healthy controls will also join the trial for 12 months (those donating blood monthly). In the other group donating blood once for blood cell characterization, they will be

invited for a single blood donation.

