8.4 Randomisation

Selection of active treatment versus control subjects will be randomised 1:1 by an independent investigator at the patient Baseline visit, with matching on demographic variables (age and sex) to optimize balance between groups. It will be obvious to the patients into which group they have been randomised.

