9.2 Participant insurance

If a participant becomes ill or is injured, they must immediately advise a member of the study team of their condition. In the first instance their study doctor will evaluate their condition and then discuss treatment with both the participant and their regular treating doctor. As this trial is not sponsored by a Company, any questions about compensation to the participants must initially be directed to the Co-ordinating Principal Investigator. It is the recommendation of the independent ethics committee responsible for the review of this trial that the participants seek independent legal advice. The University of Western Australia has provided indemnity cover for participants in this trial.

10. Study Assessments and Procedures

For the Schedule of Events, please refer to Appendix 1.

Professors [name] and [name], or other neurologists involved in the study, will be responsible for screening potential participants, gathering participant information, obtaining informed consent (or confirming it has been obtained by a member of the study team), determining eligibility for randomisation, clinical evaluation, clinical management of the participants during the course of the study, and review of all diagnostic blood tests and MRI results.

For those randomised to receive narrow band UVB phototherapy (and prior to phototherapy), [name] will obtain the patient's sun exposure history, occupation, personal and family history of skin cancer, and medications used. Upon examination, sun damage and presence of skin disease including skin cancers will be documented.

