10.3 Treatment schedule

Narrow band UVB phototherapy will be given three times/week for eight weeks (24 exposures in total). Narrow band UVB phototherapy will be delivered according to the Dundee protocol which is based on the participant's skin type. The starting dose of 20 mJ/cm² is chosen based on knowledge of the skin type and will be well below the likely erythema threshold. All participants will start with 40% increments on their initial dose, which will be reduced to 20% increments after 6 exposures. At each visit the dose given and any adverse effects will be recorded by [name], or her experienced study nurses.

[name] will assess the skin of the participants before and 6 months after initiation of phototherapy, and during the trial if the participants have any concerns.

Narrow band UVB phototherapy will be initiated as soon as possible for those who are not prescribed a short course (few days) of glucocorticoids for treatment of their first demyelinating event.

If participants randomised to receive narrow band UVB phototherapy have been given a short course of glucocorticoids to treat their symptoms, the participants will be asked to commence UVB phototherapy in one month after completion of glucocorticoids. This will allow a drug-washout period and normalization of their immunological biomarkers. After this 'washout period' and immediately prior to the start of phototherapy, they will be asked to donate 50 ml blood for pretherapy measurement of biomarkers and collection of peripheral blood mononuclear cells for functional assays.

All participants will be required to wear a UVB dosimeter for 8 weeks. The UVB dosimeters will be used to collect daily UVB exposure data for these participants.

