- Known co-morbid illnesses that might be exacerbated by phototherapy, including lupus erythematosus and xeroderma pigmentosum
- A history of melanoma, multiple non melanoma skin cancers
- Previous prolonged courses of UVB or photochemotherapy (PUVA), or use of sunbeds
- Cardiovascular or respiratory disease that would prevent standing in the treatment cubicle
- Bullous disease
- Use of photosensitizing medications
- Very fair skin that burns with very minimal sun exposure (as judged by the dermatologist involved)
- Current immunosuppressive drug therapy (beta-interferon, glatiramer acetate, natalizumab, mitoxantrone, or other chemotherapy agent specifically for demyelinating disease) prior to CIS diagnosis. (*Note that requirement for immunomodulatory therapy in the course of MS disease management will not exclude patients during follow-up; treatment variables will be collected and analysed in both the intervention and control arms in the planned analysis).
- Current pregnancy, breastfeeding or planning to become pregnant in the next 12 months.
- A second clinical demyelinating event prior to randomisation
- Concurrent diagnosis of other neurological, psychiatric or other disease, which, in the opinion of the investigator, could impair capacity to provide informed consent or interfere with study compliance.
- Current enrolment in another interventional trial

- Any contraindication to MRI scanning or intravenous Gadolinium including:
 - o Cardiac Pacemaker
 - Cardiac Defibrillator
 - o Metal fragments in the eye
 - o Any other non-MRI compatible medical device/implant or medical condition
 - o Previous allergic reaction to Gadolinium
 - o Severe claustrophobia

15. Withdrawal Criteria

Participants will be screened for adverse events during phototherapy, and will cease therapy if they experience a significant or serious adverse event, which, in the opinion of the treating neurologists (Professors [name] and [name]) or the dermatologist ([name]), is related to the treatment.

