24.8 Protocol Compliance

The instructions and procedures specified in this Protocol require diligent attention to their execution. Any participant treated in a manner that deviates from the Protocol, or who is admitted into the study but is not qualified according to the Protocol may be ineligible for analysis and thereby compromise the study.

Only when an emergency occurs that requires a departure from the Protocol for an individual will there be such a departure. The nature and reasons for the Protocol violation shall be recorded in the Case Report Form for that participant.

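### The set called intention-to-treat is defined by six UVB sessions received, so it can lose patients from the UVB arm only and does not preserve the randomised comparison

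*Protocol*

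**What the plan says.** The same sentence appears in Section 19.1 and in the synopsis under Statistical Analyses: "Participants who have undergone 2 weeks (6 sessions) of narrow band UVB phototherapy will qualify for intention-to-treat analysis". The protocol defines no other analysis set and gives no membership rule for the no-phototherapy arm.

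Allocation comes before treatment. Section 8.4 states: "Selection of active treatment versus control subjects will be randomised 1:1 by an independent investigator at the patient Baseline visit". On the control arm, Section 8.2 states: "Participants in the other group will not receive phototherapy but will wear a UVB dosimeter for 8 weeks". On the schedule, Section 10.3 states: "Narrow band UVB phototherapy will be given three times/week for eight weeks (24 exposures in total".

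Three other places bear on who is analysed:

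- **Trial exit.** Sections 8.3, 10.4.5 and 15.1 ask participants to leave the trial, with an early termination visit, if gaps between sessions mean the full course cannot be finished within 12 weeks.
- **Compliance.** Section 24.8 says that a participant treated in a way that departs from the protocol, or who is admitted but "is not qualified according to the Protocol may be ineligible for analysis and thereby compromise the study".
- **Skin examination.** The opening of Section 10 describes a sun-exposure and skin-cancer history and a skin examination with the words "For those randomised to receive narrow band UVB phototherapy (and prior to phototherapy". One exclusion in Section 14 rests on a dermatologist's judgement: "Very fair skin that burns with very minimal sun exposure (as judged by the dermatologist involved".

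**The concern.** An intention-to-treat set takes its validity from randomisation: membership is fixed at allocation and nothing that happens later can change it. Here membership is decided about two weeks into treatment, and in one arm only. A UVB patient who stops before session six, for whatever reason, leaves the analysis. A control with the same clinical course stays.

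This affects the between-arm comparison of the clinical/MRI endpoint and of the biomarker endpoints, all of which Section 8.6 lists as primary. It also introduces an asymmetry in the time-to-event analysis of Section 19.4.1. Controls are followed from randomisation (Sections 10.4.2 and 10.4.3), while UVB patients count only if they stay in treatment long enough to receive six sessions. Section 8.4 acknowledges that patients will know their group, so early stopping can itself depend on allocation.

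**Working it through.** **1. The threshold.** Three sessions a week for two weeks is 3 × 2 = 6, as stated. The full course is 3 × 8 = 24, also as stated. The figure is internally consistent; the fault lies in its use.

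**2. Who is in the set.** Planned arms are 30 and 30 (Section 19.3). Let k be the number of UVB patients with fewer than six sessions.

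- Literal reading: (30 − k) UVB v 0 controls.
- Workable reading: (30 − k) UVB v 30 controls, for example 27 v 30 for k = 3 and 24 v 30 for k = 6.
- All randomised: 30 v 30.

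**3. Routes to fewer than six sessions.** All exist in the UVB arm alone: stopping UVB for a related adverse event (Sections 8.3, 15 and 15.1); missed sessions leading to trial exit (Sections 8.3, 10.4.5 and 15.1); and a patient leaving before starting, for which the post-steroid delay gives time, since "the participants will be asked to commence UVB phototherapy in one month after completion of glucocorticoids" (Section 10.3).

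**4. How far the result can move with no true effect.** Let p be the event rate in both arms, d the share of the UVB arm removed, and q the event rate among those removed. The UVB rate seen is (p − d·q)/(1 − d).

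Inputs: p = 90% is the protocol's rate for new MRI lesions over 1.5-2 years (Section 19.3). The protocol gives no 12-month rate, so p = 70% is assumed as an alternative. The values k = 3 and 6 (d = 10% and 20%) and all values of q are assumptions. In patients, 90% of 30 is 27 events and 70% of 30 is 21.

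| p | Removed | q | UVB rate seen | Apparent effect |
|---|---|---|---|---|
| 90% | 3 | 100% | 24/27 = 88.9% | 1.1 points benefit |
| 90% | 6 | 100% | 21/24 = 87.5% | 2.5 points benefit |
| 90% | 3 | 0% | 27/27 = 100% | 10 points harm |
| 70% | 3 | 100% | 18/27 = 66.7% | 3.3 points benefit |
| 70% | 6 | 100% | 15/24 = 62.5% | 7.5 points benefit |
| 70% | 3 | 50% | 19.5/27 = 72.2% | 2.2 points harm |
| 70% | 6 | 50% | 18/24 = 75.0% | 5.0 points harm |

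For scale, Section 19.3 plans around a 10% reduction.

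**The case against.** The best defence is that a minimum-exposure set is a legitimate thing to look at, that exclusion of all controls is only loose drafting, and that a separate analysis plan may set matters right. Part of this stands. The comparisons planned in Sections 7 and 19.4 show that controls are meant to be included, so the literal reading is a wording defect and not the substance. A six-session set is also reasonable as a supportive analysis. But the protocol states this definition twice as its intention-to-treat set, so an analysis plan that used all randomised patients would contradict it.

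A reader might infer more than the document supports, on five counts:

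- *That UVB patients in the set are guaranteed event-free for two weeks.* They are not. No section removes a patient for relapse, so one who relapses and still reaches session six is kept. The MRI part of the endpoint is read only at 6 and 12 months (Section 8.6).
- *That safety is affected too.* Section 10.5 records all adverse events from consent to final follow-up, and Section 19.2 has the safety board review all those reported. Neither is tied to the six-session rule.
- *That Section 24.8 is a second UVB-only exclusion.* It covers any participant in either arm and says only that analysis may be refused.
- *That patients are removed for skin type after allocation.* Section 10.2 has all criteria confirmed before randomisation, and Appendix 1 lists a dermatologist's skin assessment in the baseline column. Section 10 describes an examination in the UVB arm and does not say that anyone is then removed. The passages need reconciling, but removal is an inference.
- *That the bias favours UVB.* The table shows that it can go either way.

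**Conclusion.** The definition is wrong as written and should be corrected before any analysis. It mislabels a minimum-exposure set as intention-to-treat and permits exclusions in one arm only, which breaks the randomised comparison for the between-arm efficacy and biomarker analyses.

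The conclusion follows from the wording alone. The size does not. With 3 or 6 UVB patients removed and no true effect, the scenarios shown range from 7.5 points of false benefit (70% event rate, six patients removed, all with events) to 10 points of false harm (90% rate, three event-free patients removed). At the protocol's own 90%, false benefit is limited to 1.1 or 2.5 points. These figures rest on assumed numbers removed and assumed event rates among them; if nobody stops before session six, the workable reading loses no one.

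**What to change.** 1. Replace the sentence in Section 19.1 and in the synopsis with: *All randomised participants are analysed in the arm to which they were randomised, whatever number of UVB sessions they receive.* Keep six or more sessions only as a set labelled supportive.
2. State in Section 24.8 that its ineligibility wording does not remove randomised participants from this set.
3. Reconcile the trial-exit rule in Sections 8.3, 10.4.5 and 15.1 with the new set. Rewording Section 19.1 does not by itself recover 12-month outcomes for those who exit. The protocol should say that outcome data already planned for them, including the MRI, blood and EDSS of the early termination visit, are used. Who should stop phototherapy is a clinical matter and no part of this point.
4. Separately, reconcile the opening of Section 10 (skin examination described for those already randomised to UVB) with Section 10.2 and Appendix 1 (criteria confirmed before randomisation, skin assessment at baseline).

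The cost is mainly wording. The estimated effect may be somewhat diluted by non-adherence, and early leavers may still have incomplete 12-month data.
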